- On-Treatment Full Analysis Set (FAS): On-Treatment FAS is the group of subjects who received at least 1 dose of lemborexant and had at least 1 postdose primary efficacy measurement. (revised per Amendment 06)
- The Per Protocol Analysis Set is the group of subjects who sufficiently complied with the protocol. Details of the evaluability criteria will be determined before database lock and treatment unblinding and will be specified in the Statistical Analysis Plan (SAP). (revised per Amendment 01)
- The 6-Months Completer Analysis Set is the group of subjects in the FAS who had all efficacy assessments up to and including Month 6 (ie, Week 1 and Months 1 to 6 visits) without missing primary or key secondary efficacy assessments at any of these visits. (revised per Amendment 04)
- The PK Analysis Set is the group of subjects who had at least 1 quantifiable lemborexant plasma concentration or its metabolites, with adequately documented dosing history.
- The PK/PD Analysis Set is the group of subjects receiving either lemborexant or PBO who have efficacy or safety data with documented dosing history. In addition, subjects receiving lemborexant should have at least 1 quantifiable lemborexant concentration data point as per the PK Analysis Set.

Efficacy Analyses

Definitions of Baseline

For the analyses of PBO-controlled endpoints (ie, Day 1 to Month 6), “Study Baseline” when applied to analysis endpoints is defined as the data captured during the Run-In Period (or during the Baseline Period). For the analyses of data that are not placebo-controlled (ie, Month 7 to Month 12), data from Month 6 will be used as the “Period 2 Baseline”. (revised per Amendment 06)

For other endpoints, baseline data are captured during the Run-In and Baseline Period. Details will be specified in the SAP. (revised per Amendment 01)

12-Month Lemborexant Exposure

Twelve-month (12-month) lemborexant exposure summaries will be summarized by treatment (LEM5, LEM10) and duration of exposure (1 month [30 days] where appropriate, 3 months [90 days], 6 months [180 days], 9 months [270 days] and 12 months [365 days]). Treatment groups are LEM5 and LEM10, and include both (a) LEM Period 1 subjects on the On-Treatment Full Analysis Set using the change from Study Baseline and (b) LEM Period 2 subjects previously receiving PBO

on the On-Treatment Full Analysis Set using the change from Period 2 Baseline. (revised per Amendment 06)

Control of Type 1 Error

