9 INVESTIGATIONAL PLAN

9.1 Overall Study Design and Plan

This study is a 12-month, multicenter, randomized, controlled, double-blind, parallel-group study of 2 doses of lemborexant in approximately 900 male or female subjects with insomnia disorder (subjects who complain of difficulties with sleep onset and/or sleep maintenance). Approximately 40% of the population will be 65 years of age or older. Note: enrollment of subjects <65 years may be limited if the percentage of enrolled subjects ≥ 65 years is below expectations toward the end of the study. (revised per Amendments 01 and 03)

The study will have 2 phases, the Prerandomization Phase and the Randomization Phase. The Prerandomization Phase will comprise 3 periods and last up to 35 days: a Screening Period, a Run-In Period and a Baseline Period. The Randomization Phase will comprise a 6-month, placebo-controlled treatment period (Period 1). During the next 6 months (Period 2), subjects will receive only active treatment. Subjects will be informed that they will receive PBO at some point during the study and that all will receive active drug for at least 6 months. They will not be informed of either the timing of these periods or the timing of the 2nd randomization. A 2-week Follow-Up Period will then take place, followed by an End of Study Visit. (revised per Amendment 03)

End of Study

The end of the study will be the date of the last study visit for the last subject. As required by some regulatory agencies, the following estimates are provided:

- The study will begin enrollment in approximately November 2016 (revised per Amendments 01 and 03)
- The estimated duration for each subject on study is anticipated to be a maximum of 60 weeks (a maximum 35-day Prerandomization Phase [that includes a Screening Period, a maximum 17-day Run-In Period, and a Baseline Period] + 52 weeks of the Randomization Phase + a 1-week window + a 2-week Follow-Up Period). (revised per Amendment 03)
- Approximately 900 subjects with insomnia disorder (18 years or older) will be randomized to receive LEM5 or LEM10 or PBO for 6 months. After 6 months, subjects who previously received lemborexant will continue to receive lemborexant at the same dosage level for an additional 6 months, while subjects who previously received PBO will undergo a 2nd randomization to receive LEM5 or LEM10 for 6 months.

An overview of the study design is presented in [Figure 1](#).

[figure not shown]

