1.1.3 Exploratory Objectives

The following will be explored for both LEM5 and LEM10 compared to PBO over Period 1 and over Period 2 with analyses dependent on whether subjects received active treatment or PBO during Period 1:

- Efficacy on quality of sleep
- Health outcomes on the EuroQOL version 5D-3L (EQ-5D-3L), Work Productivity and Activity Impairment Questionnaire – General Health (WPAI-GH), and Patient Global Impression – Insomnia (PGI-Insomnia)
- Efficacy on sSOL, sSE, sWASO, sTST, ISI, and FSS
- Withdrawal symptoms after completion of treatment (Period 2 only)

The following will be explored for LEM5 and LEM10:

- Plasma concentrations of lemborexant and its metabolites M4, M9, and M10
- Population pharmacokinetic (PK) modeling for lemborexant
- PK/pharmacodynamic (PD) relationships between lemborexant concentrations and efficacy and safety variables

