	-11	241	723	323	969
	-11.4	225	675	300	900
	-12	203	609	271	813

CfB = change from baseline, sSOL = subjective sleep onset latency, sWASO = subjective wake after sleep onset.

The study also had adequate power for the secondary analysis of responders. A sleep onset responder was defined as follows: sSOL at Study Baseline was ≥ 30 minutes and mean sSOL at 6 months was ≤ 20 minutes, and a sleep maintenance responder was defined as follows: sWASO at Study Baseline was ≥ 60 minutes and mean sWASO at 6 months was ≤ 60 minutes and showed a reduction of > 10 minutes compared to Study Baseline. A total of 900 subjects gave >99% power to detect a treatment difference in sleep onset responder rates of 16% and sleep maintenance responder rates of 24.4%, both compared with placebo.

The above sample size also met regulatory safety requirements. Even with early discontinuation rates as high as 50% at Month 6 (ie, 150 subjects remaining) and 60% by Month 12 (ie, 120 subjects remaining in each treatment group), the requirement for 100 subjects in each of the elderly and non-elderly age-groups to complete 12-months of treatment on 5 or 10 mg lemborexant would be met. In addition, a total of 420 subjects would complete 6 months of treatment with 5 or 10 mg lemborexant.

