3.4 Efficacy Analyses

Efficacy analyses for Treatment Period 1 will be performed on the FAS unless otherwise specified. Different baseline values will be used for endpoints defined during Treatment Period 1 (ie, Day 1 to Month 6) and during Treatment Period 2 (ie Month 7 to Month 12). Baseline values for each efficacy parameter are specified in [Section 6.1.1](#). The On-Treatment FAS will be used for the on treatment summaries produced by time on treatment.

Unless specified otherwise, all efficacy endpoints will be derived by calculating the average of weekly (7 days) diary parameter values ([Section 6.1](#)).

12-month LEM exposure data will be summarized by treatment (LEM5, LEM10) and duration of exposure (1 month [30 days], 3 months [90 days], 6 months [180 days], 9 months [270 days] and 12 months [365 days]). Treatment groups are LEM5 and LEM10, and include both (a) LEM Period 1 subjects on the On-Treatment Full Analysis Set using the change from Study Baseline and (b) LEM Period 2 subjects previously receiving PBO on the On-Treatment Full Analysis Set using the change from Period 2 Baseline. No hypothesis test will be performed for efficacy endpoints beyond the Month 6 visit.

The primary and key secondary endpoints comparisons are tested following the gate-keeping testing procedure described in [Section 3.3.3](#) to control for the overall type I error at the 0.05 significance level. The first primary efficacy endpoint comparison will be performed at the 0.05 significance level. The subsequent testings will only proceed if the previous test is statistically significant at the 0.05 level.

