3.4.2.4 Other Secondary Efficacy Analyses

For all other secondary endpoints described below, the continuous variable will be summarized by using descriptive statistics by time point and the categorical variable will be summarized as the number and percentage of subjects by time point.

Unless is covered from the same model from the primary and secondary efficacy endpoints, or specified otherwise, the change from baseline assessments will be analyzed using MMRM assuming MAR (no missing value imputation) and the portion of responders will be analyzed using the Cochran Mantel Haenszel (CMH) test adjusted for region and age group. Missing values will be considered as non-responders in all responder analyses. No multiplicity adjustment will be made for all analyses.

The following endpoints will be analyzed.

EFFICACY MEASURES DERIVED FROM THE SLEEP DIARY

- Change from Study Baseline of mean sSOL, mean sSE, mean sWASO and mean sTST for the 1st 7 nights, Months 1, 2, 3, 4 and 5; and mean sTST at Month 6; for LEM5 and LEM10 compared to PBO
- Change from Study Baseline/ Treatment Period 2 Baseline of mean sSOL, mean sSE, mean sWASO and mean sTST for 1, 3, 6, 9 and 12 months exposure to LEM5 and LEM10. . Data from subjects randomized to LEM5 or LEM10 at the start of the study will use Study Baseline, data from subjects who were re-randomized to LEM5 or LEM10 in Period 2 will use Treatment Period 2 Baseline.
- The proportion of responders, separately for sSOL and sWASO, will be analyzed, for the first 7 nights, Months 1, 2, 3, 4, 5 and 6 for LEM5 and LEM10 compared to PBO:
 - The sleep onset responder is defined as: sSOL at Study Baseline is >30 minutes and mean sSOL at each month (first 7 nights, Months 1, 2, 3, 4, 5, 6) is ≤ 20 minutes,
 - The sleep maintenance responder is defined as: sWASO at Study Baseline is >60 minutes and mean sWASO at each month (first 7 nights, Months 1, 2, 3, 4, 5, 6) is ≤ 60 minutes and shows a reduction of >10 minutes compared to Study Baseline.

The proportion of responders will be analyzed based on the subjects with sSOL > 30 minutes at the baseline for sSOL and separately the subjects with sWASO > 60 minutes at the baseline for sWASO.

- The proportion of responders, separately for sSOL and sWASO, at Months 7, 8, 9, 10, 11 and 12 will also be summarized by using two types of baseline (ie., Study Baseline, Period 2 Baseline). The definition of the responder at Month 7, 8, 9, 10, 11 and 12 will be as follows:

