The same analyses for persistence versus loss of effect over Period 2 will compare sSOL, sSE, sWASO, and sTST at Months 7 through 12 to these measures at Month 7 for only the subjects who were randomized to PBO in Period 1 and who continued into Period 2. At each month beyond Month 7, the change from Treatment Period 2 Baseline will be compared to either the lower bound of the 95% CI (for sSE and sTST) or the upper bound of the 95% CI (for sSOL and sWASO) at Month 7. Persistence of effect will be defined as present if the mean change from Treatment Period 2 Baseline at Month 12 is above the lower bound of the 95% CI at Month 7 for sSE or sTST and below the upper bound of the 95% CI at Month 7 for sSOL and sWASO.

Analyses for persistence versus loss of effect over duration of exposure will be conducted for On-Treatment Full Analysis Set subjects. These analyses will compare 1 month of duration of exposure of sSOL, sSE, sWASO and sTST at 3 and 6 months duration of exposure, for a) LEM Period 1 subjects using the change from Study Baseline and (b) LEM Period 2 subjects previously receiving PBO using the change from Period 2 Baseline. At 3 and 6 months duration of exposure, the change from Study Baseline/Treatment Period 2 Baseline will be compared to either the lower bound of the 95% CI (for sSE and sTST) or the upper bound of the 95% CI (for sSOL and sWASO) at 1 month duration of exposure. Persistence of effect will be defined as present if the mean change from Study Baseline/Treatment Period 2 Baseline at 6 months of exposure is above the lower bound of the 95% CI at 1 month of exposure for sSE or sTST and below the upper bound of the 95% CI at 1 month of exposure for sSOL and sWASO.

INSOMNIA SEVERITY INDEX AND FATIGUE SEVERITY SCALE

The following endpoints will be analyzed for the ISI and FSS:

- Change from Study Baseline of the total score from items 1-7, and items 4-7, separately, on the ISI at Months 1, 3, 6 of LEM5 and LEM10 compared to PBO.

- Change from Study Baseline and Treatment Period 2 Baseline (as appropriate) of the total score from items 1-7, and items 4-7, separately, on the ISI for subjects with 3, 6, 9 and 12 months of exposure.
- Change from Study Baseline on the FSS score at Months 1, 3, 6 of LEM5 and LEM10 compared to PBO
- Change from Study Baseline and Treatment Period 2 Baseline (as appropriate) on the FSS score for subjects with 3, 6, 9 and 12 months of exposure.

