6.1.3 Visit Windowing

For the Sleep Diary, the following visit windowing rule in [Table 9](#) will be applied based on measurements from unscheduled visits and early termination visits to attain the measurement for analysis for the given scheduled visit.

Table 9 Windowing Rules for Efficacy Endpoints from Sleep Diary

Visit	Target Visit Day (in study days)	Visit Window (in study days)
First 7 nights	2	2 - 8
Visit 4 (Month 1)	30	24 - 30
Visit 5 (Month 2)	60	54 - 60
Visit 6 (Month 3)	90	84 - 90
Visit 7 (Month 4)	120	114 - 120
Visit 8 (Month 5)	150	144 - 150
Visit 9 (Month 6)	180	174 - 180 (or last 7 days prior to subject entering Period 2, whichever is earlier) *

Table 9 Windowing Rules for Efficacy Endpoints from Sleep Diary

Visit	Target Visit Day (in study days)	Visit Window (in study days)
Visit 10 (Month 7)	210	204 - 210
Visit 11 (Month 8)	240	234 - 240
Visit 12 (Month 9)	270	264 - 270
Visit 13 (Month 10)	300	294 - 300
Visit 14 (Month 11)	330	324 - 330
Visit 15 (Month 12)	364	Last 7 days from study days 358 - 371 (or last dose date + 1 for subjects who completed 12 months treatment, whichever is earlier)

*: If subjects discontinued the study and did not enter Treatment Period 2, last 7 days from study days 168 -180 will be used.

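### The 12-month exposure efficacy summaries place Day-1 lemborexant subjects and former-placebo subjects, measured from different baselines, in one group per dose, and only the Day-1 subjects can reach the 9- and 12-month columns

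*SAP*

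**What the plan says.** SAP 3.4 defines the 12-month exposure groups by dose, with columns at 30, 90, 180, 270 and 365 days. Each dose group has two parts. Cohort (a) took lemborexant from Day 1 and is measured as change from Study Baseline. Cohort (b) is described as "b) LEM Period 2 subjects previously receiving PBO on the On-Treatment Full Analysis Set using the change from Period 2 Baseline". The Protocol Synopsis has the same rule ("on the On-Treatment Full Analysis Set using the change from Period 2 Baseline"), as does Protocol 9.7.1.6.

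SAP 3.4.2.4 repeats it for sSOL, sSE, sWASO and sTST: "data from subjects who were re-randomized to LEM5 or LEM10 in Period 2 will use Treatment Period 2 Baseline". The ISI and FSS summaries, for example "on the FSS score for subjects with 3, 6, 9 and 12 months of exposure", and the sleep-quality summary in SAP 3.8 also take whichever of the two baselines applies. The exposure-based persistence analysis in SAP 3.4.2.4 compares 3 and 6 months of exposure with 1 month for both cohorts and does not say whether they are combined.

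Cohort (b) has six months of lemborexant by design. Protocol 9.1 has Day-1 lemborexant subjects continue on their dose, "while subjects who previously received PBO will undergo a 2nd randomization to receive LEM5 or LEM10 for 6 months". In SAP Table 9 the final diary window is "Last 7 days from study days 358 - 371".

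**The concern.** The two cohorts' changes are not the same quantity. Any change that would have occurred on placebo after Study Baseline is part of cohort (a)'s change, but for cohort (b) it is already in the Month 6 baseline. The cohorts also leave the table at different points, because (b) cannot contribute beyond about six months of exposure. Moving from the 6-month to the 9-month column therefore changes both who is averaged and what is averaged.

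This matters because persistence over 12 months is a stated secondary objective. For ISI, FSS and sleep quality, the SAP carries results past Month 6 only through these exposure summaries. If the placebo-phase change is an improvement and the drug effects are similar, the step looks like further gain and could mask some loss of effect. Other combinations push it the other way.

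**Working it through.** **1. Reproduce the plan's count.** SAP Section 2 assumes 300 per arm, with 50% discontinued at Month 6 and 60% by Month 12, and concludes: "In addition, a total of 420 subjects would complete 6 months of treatment with 5 or 10 mg lemborexant".

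- Cohort (a): 300 × 0.50 = 150 per dose, 300 over both doses.
- Former placebo at Month 12: 300 × 0.40 = 120, or 60 per dose under the 1:1 second randomisation.
- Total: 300 + 120 = 420, as stated. The plan's own count at six months of exposure thus includes both cohorts.

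**2. How long cohort (b) can be exposed.** Period 2 starts at about study day 180, and Table 9 ends at day 371. Protocol Table 3 allows ±7 days at Months 6 and 12.

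- On schedule: 364 − 180 = 184 days.
- Longest: 371 − 180 = 191 days, or 371 − 173 = 198 days if Month 6 is 7 days early.
- Shortest for a completer within windows: 357 − 187 = 170 days.

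No one in (b) reaches 270 days, and some completers may fall short of 180.

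**3. Share of cohort (b), w.**

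- 6 months, SAP dropout: 60/(150 + 60) = 60/210 = 0.286.
- 6 months, no dropout: 150/(300 + 150) = 150/450 = 0.333.
- If only half of (b)'s completers reach the 180-day column (assumed): 30/180 = 0.167 with SAP dropout, 75/375 = 0.200 without.
- 9 and 12 months: 0 in every case.

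**4. The shift.** Count improvement as positive. Let P be the further placebo-phase change after Study Baseline, and Da and Db the two cohorts' drug effects. Assume effects add and stay constant, and that dropout is not selective.

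- Pooled 6-month mean = (1 − w)(Da + P) + w·Db.
- 9-month mean = Da + P.
- Shift, 9 minus 6 months = w(P + Da − Db), which is w·P when Da = Db.

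The documents do not give P. Illustration for sSOL in raw minutes, where 4.35 is half the 8.7-minute planning difference:

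| P (assumed) | Db − Da (assumed) | Shift, w = 0.286 | Shift, w = 0.333 |
|---|---|---|---|
| 0 | 0 | 0 | 0 |
| 5 | 0 | 1.43 | 1.67 |
| 10 | 0 | 2.86 | 3.33 |
| 20 | 0 | 5.71 | 6.67 |
| 0 | +4.35 | −1.24 | −1.45 |
| 0 | −4.35 | +1.24 | +1.45 |
| 10 | +4.35 | 1.61 | 1.88 |
| 10 | −4.35 | 4.10 | 4.78 |

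The change of composition in step 3 needs no assumption about P; only the size and direction of the shift do.

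**The case against.** - **A split may be intended.** Protocol 9.7.1.6.3 and the Synopsis, describing the 12-month exposure summaries, match the two baselines to Period 1 and Period 2 data respectively, which could mean a separate mean and interval for each. The table shells are a separate document (SAP Section 9) and may already separate the cohorts. This stands as a possibility, but that wording assigns baselines without clearly splitting the means, and the SAP text states no split.
- **The consequence is limited.** SAP 3.4 rules out hypothesis tests past Month 6. For sSOL, sSE, sWASO and sTST, SAP 3.4.2.4 also has a by-visit persistence analysis from Study Baseline and one restricted to former-placebo subjects from Month 7. For ISI, FSS and sleep quality, cohort (a)'s course can be pieced together from the Period 1 Month 6 tables and the later exposure columns. All of this stands, though a reader must know to do the piecing together.
- **P may be small.** SAP 6.1.1 takes the diary Study Baseline from the last 7 mornings of the placebo run-in, so P is only the further change after that. Protocol 9.2.2 refers to large placebo effects in insomnia trials, but the run-in may absorb much of them. This stands.
- **The fall in n would be visible.** It would, but it could be taken for ordinary dropout, and it does not show that the baseline changed too.
- **The grouping is protocol text as well.** True, so the remedy should add to the specified grouping rather than remove it.

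**Conclusion.** The point holds as a matter of presentation. As written, the exposure summaries mix two quantities through 6 months and change composition before 9 months. Cohort (b) is about 29% to 33% of the 6-month column if all its completers reach it, less if Period 2 runs under 180 days, and nil afterwards. The resulting shift is w(P + Da − Db). Its size and sign are unknown from the documents, and it is zero if P is zero and the drug effects are equal.

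A reader might infer three stronger things that the documents do not support:

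- **That the efficacy conclusions are compromised.** The confirmatory tests are all at Month 6 in the placebo-controlled period and do not use these groups.
- **That a distortion of several minutes in sSOL is established.** The minutes above follow from assumed values of P.
- **That SAP 3.4 contradicts SAP 1.1.3**, which calls for Period 1 and Period 2 to be explored "with analyses dependent on whether subjects received active treatment or PBO during Period 1". The SAP does supply cohort-specific analyses in 3.4.2.4, so one summary that varies only the baseline does not breach that objective.

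**What to change.** In the change-from-baseline efficacy exposure summaries (SAP 3.4, 3.4.2.4 and 3.8) and the exposure-based persistence analysis (SAP 3.4.2.4):

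- Present cohorts (a) and (b) separately, each with its n and its baseline named.
- Label the 9- and 12-month columns as cohort (a) only.
- If the protocol-specified pooled column is kept, show it only beside the two cohort columns, with a footnote on the two baselines.
- Record the addition in SAP Section 5.

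If the table shells already do this, a confirming sentence in the SAP is enough. No new data are needed. The cost is SAP wording, more columns and smaller numbers in each: for example, 150 and 60 rather than 210 per dose at 6 months under the SAP's dropout scenario.

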3.4.1 Primary Efficacy Analyses

The primary efficacy endpoint is the change from Study Baseline of sSOL at Month 6 of LEM10 and LEM5 compared to PBO.

Null Hypothesis: No difference exists in the mean change from Study Baseline to Month 6 of treatment with LEM10 (or LEM5) as compared with PBO.

Alternative Hypothesis: For sSOL, a difference exists in the mean change from Study Baseline to Month 6 for LEM10 (or LEM5) as compared with PBO.

The sSOL change from Study Baseline to Month 6 will be analyzed using the mixed effect model repeated measurement (MMRM) analysis on the FAS. The model will be adjusted for the corresponding Study Baseline value, region (North America, Europe and New Zealand, Asia), age group (<65 years old, ≥65 years old), treatment, time (1st 7 nights, Month 1, Month 2, Month 3, Month 4, Month 5 and Month 6) and the interaction of treatment by time. Since the sSOL is known to be non-normally distributed, a log-transformation will be used in the analysis.

The unstructured covariance matrix (UN) will be used in the analysis. In the case of non-convergence of UN, the toeplitz covariance matrix (TOEP) will be used. In the case of non-convergence with TOEP, the autoregressive covariance matrix [AR (1)] will be used in the model.

Before the implementation of the MMRM model, the missing values will be imputed using a pattern mixture model utilizing multiple imputation (MI) assuming the missing values are missing not at random (MNAR) utilizing the complete case missing value pattern (CCMV - subjects who completed all primary efficacy assessments without missing values). The missing values for a given visit will be imputed using all available values including the retrieved measurement from the post-discontinuation data.

The treatment comparison will be performed using contrasts. The p-value, least square (LS) means and the 95% confidence interval (CI) for the treatment difference will also be provided.

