9.7.1.6.1 ANALYSIS FOR THE PRIMARY ENDPOINT

Null Hypothesis: For sSOL, no difference exists in the mean change from Study Baseline to Month 6 of treatment with LEM10 and LEM5 as compared with PBO.

Alternative Hypothesis: For sSOL, a difference exists in the mean change from Study Baseline to Month 6 for LEM10 and LEM5 as compared with PBO.

The sSOL change from Study Baseline to Month 6 will be analyzed using the mixed effect model repeated measurement (MMRM) analysis on the FAS. The model will include all data and will be adjusted for the corresponding Study Baseline value, region, age group (<65 years old, ≥65 years old), treatment, time (average of the first 7 nights, Month 1, Month 3, and Month 6) and the interaction of treatment by time. An unstructured covariance matrix will be used, and if the model fails to converge, then an autoregressive matrix will be used. The missing values will be imputed using a pattern mixture model utilizing multiple imputation (MI) assuming the missing values are missing not at random (MNAR) utilizing the complete case missing value pattern (CCMV - subjects who completed all primary efficacy assessments without missing values). (revised per Amendment 04) The missing values for a given visit will be imputed using all available values including the retrieved measurement from the post-discontinuation data. The treatment comparison will be performed using contrasts. The p-value, least square (LS) means and the 95% confidence interval (CI) for the treatment difference will also be provided. Details of pattern mixture model and MI method will be presented in SAP. (revised per Amendment 03)

The following analyses will be considered as sensitivity analyses (revised per Amendment 04):

- Missing imputation assuming MNAR utilizing CCMV-7: The same MMRM method used in the primary analysis will be applied utilizing CCMV-7 (ie, up to 7 monotone missing patterns will be used for missing value imputation). (revised per Amendment 04)
- Tipping point analysis: A range of shifts starting from the primary analysis (CCMV) will be used in the multiple imputation of missing data assuming MNAR to identify the specific shift and treatment effect that will tip the results from statistically significant to non-significant. (revised per Amendment 04)

The following analyses will be considered as supplementary analyses (revised per Amendment 04):

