3.4.1.1 Multiple Imputation

Step 1 (imputing missing data): Thirty multiple imputed complete datasets were to be constructed using imputation regression model of baseline sSOL, baseline ISI, age, sex, race (white, black, and other), and region (North America, Europe and New Zealand, Asia), baseline BMI, baseline log(sSOL), baseline ISI with a predefined arbitrary seed number (seed=2006). SAS PROC MI will be used to implement the imputation procedure using all available values. The dataset will be converted into monotone missing pattern by imputing arbitrary missing data as the first step. The monotone data will then be imputed with monotone regression method and MNAR. The sample SAS statement can be found in [Section 7](#).

Step 2 (performing MMRM using each imputed dataset): The MMRM model with factors of age group (<65 years old, ≥65 years old), region (North America, Europe and New Zealand, Asia), treatment, visit (1st 7 nights, Month 1, Month 2, Month 3, Month 4, month 5 and Month 6), and treatment-by-visit interaction as fixed effect, and the baseline log(sSOL) as a covariate will be applied to each imputed dataset. SAS PROC MIXED will be used for the MMRM analysis. The sample SAS statement can be found in [Section 7](#).

Step 3 (combine results): Resulting treatment effect parameter estimators and standard errors from each of 30 multiple imputed datasets from Step 2 will be combined using SAS PROC MIANALYZE to obtain the pooled treatment effect and variance parameter estimators according to Rubin's rules ([Rubin DB, 1987](#)). The sample SAS statement can be found in [Section 7](#).

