7 PROGRAMMING SPECIFICATIONS

The rules for programming derivations and dataset specifications are provided in separate documents.

The following sample SAS statement provides the framework for the MI method:

CONVERT DATASET INTO MONOTONE MISSING DATA PATTERN (IMPUTING ARBITRARY MISSING DATA):

```
PROC MI data=<dataset> nimpute=30 seed=2006 out=<dataset1>;
  VAR age BMI baseline... visit1-visit8;
  MCMC chain=multiple nbiter=500 niter=300 impute=monotone;
  BY treatment;
RUN;
```

IMPUTE MISSING VALUES:

```
PROC MI data=<dataset1> nimpute=1 seed=2006 out=<dataset2>;
  CLASS treatment sex race region;
  MONOTONE regression (/details);
  MNAR model (visit2-visit8/ modelobs=CCMV);
  VAR treatment age sex race region BMI baseline....;
  BY _imputation_;
RUN;
```

PERFORMING MMRM:

```
PROC MIXED data=<dataset2>;
  CLASS subject treatment agegrp visit;
  MODEL value=treatment agegrp region visit visit*treatment / ddfm=kr;
  REPEAT visit/sub=subject type=UN;
  LSMEANS visit*treatment/DIFF CL;

  BY _imputation_;
  ODS output estimates=<dataset3>;
RUN;
```

COMBINE RESULTS:

```
PROC MIANALYZE data=<dataset3>;
  MODELEFFECTS estimate;
  STDERR stderr;
RUN;
```

VARIABLE ORDER TO BE USED IN THE PROC MI PROCEDURES:**To Create Monotone Missing Data Pattern**

- sSOL: age, baseline BMI, baseline ISI, baseline log(mean sSOL), log(mean sSOL) at first 7 nights, log(mean sSOL) at Month 1, log(mean sSOL) at Month 2, log(mean sSOL) at Month 3, log(mean sSOL) at Month 4, log(mean sSOL) at Month 5, log(mean sSOL) at Month 6

- sSE: age, baseline BMI, baseline ISI, baseline mean sSE, mean sSE at first 7 nights, mean sSE at Month 1, mean sSE at Month 2, mean sSE at Month 3, mean sSE at Month 4, mean sSE at Month 5, mean sSE at Month 6
- sWASO: age, baseline BMI, baseline ISI, baseline mean sWASO, mean sWASO at first 7 nights, mean sWASO at Month 1, mean sWASO at Month 2, mean sWASO at Month 3, mean sWASO at Month 4, mean sWASO at Month 5, mean sWASO at Month 6
- sTST: age, baseline BMI, baseline ISI, baseline mean sTST, mean sTST at first 7 nights, mean sTST at Month 1, mean sTST at Month 2, mean sTST at Month 3, mean sTST at Month 4, mean sTST at Month 5, mean sTST at Month 6

To Impute Missing Values

- sSOL: treatment, sex, race, region + variables used to create monotone missing data pattern
- sSE: treatment, sex, race, region + variables used to create monotone missing data pattern

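### The primary and key secondary MMRMs fit one baseline slope to all visits; a baseline-by-visit term would protect Month 6 precision at very little cost

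*SAP*

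**What the plan says.** SAP 3.4.1 adjusts the primary MMRM for Study Baseline, region, age group, treatment and time, and closes the list with "Month 4, Month 5 and Month 6) and the interaction of treatment by time". Step 2 of 3.4.1.1 restates the model: "and treatment-by-visit interaction as fixed effect, and the baseline log(sSOL) as a covariate will be applied to each imputed dataset". Section 3.4.2.1 gives the same structure for sSE and for sWASO, each with its own baseline. Protocol 9.7.1.6.1 and the synopsis have the same form with four time points: "Month 1, Month 3, and Month 6) and the interaction of treatment by time". No baseline-by-visit term appears in either document.

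Three other provisions bear on the point.

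- Covariance (SAP 3.4.1): "The unstructured covariance matrix (UN) will be used in the analysis", with Toeplitz and then AR(1) as fallbacks.
- Missing data (SAP 3.4.1): "Before the implementation of the MMRM model, the missing values will be imputed using a pattern mixture model". The primary MMRM therefore runs on completed data.
- Section 7: the sSOL imputation order includes "baseline log(mean sSOL), log(mean sSOL) at first 7 nights" and then each month in turn, so imputation does not impose a common slope. The sample MMRM code reads "MODEL value=treatment agegrp region visit visit*treatment / ddfm=kr", with no baseline term.

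**The concern.** The model lets the treatment effect differ at every visit but holds the baseline effect constant from the first 7 nights to Month 6. The fitted slope is a compromise across visits, while Month 6 is the only visit used for confirmatory testing. Baseline lies about a week before the first visit and six months before the last, so a weakening association is plausible. The SAP gives no reason for assuming a constant one.

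What is at stake is precision on six tests. The first, LEM10 on sSOL, controls all the others. SAP Section 2 sizes 300 per arm for -8.7 min but quotes a Study 201 median difference of about -6.8 min for LEM10. Table 2 asks for 371 per group to reach 80% power at that difference.

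**Working it through.** **1. The plan's own figure.** For sSOL (SAP Section 2: difference -8.7 min, SD 33, two-sided 0.05, 90% power):

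n = 2 × [33 × (1.960 + 1.282) / 8.7]² = 302.4, so 303 per group against 300 stated.

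Power at 300 = Φ(8.7 / (33√(2/300)) − 1.96) = Φ(8.7/2.694 − 1.96) = 89.8%.

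For sWASO (-11.4 min, SD 43) the result is 299 against 300, with power 90.1%. The plan reproduces. Both SDs are SDs of raw change, so the plan takes no credit for baseline adjustment.

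**2. Effect of a common slope.** With complete data and free treatment-by-visit terms, the Month 6 contrast is D6 − b_c × D0. D6 is the arm difference in mean Month 6 value, D0 the chance baseline difference and b_c the common slope. Using change as the response shifts every slope by 1 and leaves this result as it is. Relative to a Month 6 slope b6:

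variance ratio = 1 + (b6 − b_c)² × Var(baseline) / residual variance at Month 6.

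Under an unstructured covariance, b_c = (1′S⁻¹b) / (1′S⁻¹1), where S is the residual covariance and b the vector of visit slopes.

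**3. Assumptions.** The documents give no baseline-to-visit slopes or correlations, so the following are assumed: equal SDs, so that the standardized slope equals the correlation ρ; slopes linear in time from 0.8 at Week 1; and residual correlation between visits either AR-type (0.6 to 0.8 between adjacent visits) or constant (0.6 to 0.8). Region and age are ignored. With ρ the Month 6 correlation and 33 min the SD of change, residual variance = 33² × (1 + ρ)/2.

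Worked case, 0.8 to 0.5: residual variance = 1089 × 0.75 = 816.75 and SE = √(816.75 × 2/300) = 2.333.

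- AR-type, 0.6: b_c = 0.694; ratio = 1 + (0.194)²/0.75 = 1.050.
- Constant, 0.8: b_c = 0.922; ratio = 1 + (0.422)²/0.75 = 1.237.

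At -8.7 min, visit-specific power = Φ(8.7/2.333 − 1.96) = 96.2%. At ratio 1.237 the SE is 2.595 and power is 91.8%.

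| Slope, Week 1 to Month 6 | Variance ratio | Power at -8.7 min: visit-specific / common | Power at -6.8 min: visit-specific / common |
|---|---|---|---|
| 0.8 to 0.8 | 1.000 | 92.6 / 92.6 | 75.8 / 75.8 |
| 0.8 to 0.7 | 1.007-1.022 | 93.8 / 93.4-93.7 | 78.2 / 77.3-77.9 |
| 0.8 to 0.6 | 1.024-1.106 | 95.1 / 93.0-94.6 | 80.6 / 76.5-79.6 |
| 0.8 to 0.5 | 1.050-1.237 | 96.2 / 91.8-95.3 | 83.0 / 74.5-81.2 |

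**4. Bias and type I error.** Simulation of the common-slope model (2000 trials per scenario, 300 per arm, unstructured covariance) gave mean estimates of -8.75 to -8.64 for a true -8.7, and null rejection of 4.0% to 5.6%. Simulated variance ratios were 1.00 with equal slopes, 1.02-1.03 for correlation 0.70 falling to 0.50, and 1.13-1.14 for 0.75 to 0.35.

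**5. Section 7 code as printed.** If the analysed value is change from baseline and no baseline term is fitted, the ratio to visit-specific adjustment is 2/(1 + ρ): 1.25 at ρ = 0.6 and 1.33 at ρ = 0.5. Power at -8.7 min returns to 89.8%.

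**The case against.** The strongest reply is that the prespecified model is valid and the loss may be nil. Most of this stands, and it rules out several stronger readings.

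- **That Month 6 is adjusted with the wrong slope.** A reader might infer this as fact. The documents contain no slope or correlation, and with equal slopes nothing is lost.
- **That the treatment estimate is biased.** Randomization keeps the contrast unbiased, and the unstructured residual variance absorbs the misfit. For one particular baseline imbalance the adjustment can be slightly off, but that is the same slope-gap term already counted in the variance. In the 0.8 to 0.5 case, with SD 33, a one-standard-error imbalance is 33√(2/300) = 2.69 min. It moves the estimate by 0.194 × 2.69 = 0.5 min to 0.422 × 2.69 = 1.1 min.
- **That the design has no spare power.** At -8.7 min this fails, because planning used the unadjusted SD of change. SAP Section 2 also gives more than 99% power for sSE. At -6.8 min the margin really is thin: unadjusted power is Φ(6.8/2.694 − 1.96) = 71.4%.
- **That imputation and analysis models conflict.** The imputation model is the less restrictive of the two, which is generally the safer direction. No harm follows from the documents.

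The objection also holds that no exact size can be given. The same 0.8 to 0.5 slopes yield 5% or 24% inflation depending on residual correlation, and no log-scale SD or effect is stated. What survives is that the added term is near-neutral if slopes are equal and recovers precision if they are not.

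**Conclusion.** The concern holds as a question of efficiency, not validity. The primary and both key secondary models impose one baseline slope on seven visits. If slopes change over time, Month 6 precision is lost: 0% with equal slopes and about 1-2%, 2-11% or 5-24% of variance as the assumed Month 6 slope falls to 0.7, 0.6 or 0.5. Power losses are about 0 to 4 points at -8.7 min, always above the planned 90% in these scenarios, and about 0 to 9 points at -6.8 min. A much steeper fall (correlation 0.80 to 0.30, linear, with high post-baseline correlation) gave a ratio of 1.68 and 87% power at -8.7 min; that case is extreme.

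All sizes rest on assumed correlations and the minute scale. They carry over to log(sSOL) only if correlations are similar there. The statement on type I error is for the unstructured covariance and was not checked for the fallbacks. Over the slopes in the table, the missing baseline term in the Section 7 code would be the larger precision risk if that code were run as printed.

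**What to change.** Before unblinding:

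- Add a baseline-by-visit interaction to the MMRMs in SAP 3.4.1, 3.4.1.1 Step 2 and 3.4.2.1 (sSE and sWASO), and to the MAR MMRMs in 3.4.1.4, 3.4.2.3 and 3.4.2.4.
- Correct the Section 7 MODEL statement so that it contains baseline and baseline*visit, and list region in the CLASS statement.
- Record the change in SAP Section 5 as a departure from the model wording in protocol 9.7.1.6.1 and the synopsis.

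The cost is 6 extra parameters (7 visits less 1) against about 900 subjects, a wording change and a documented deviation from the protocol model. No new data are needed.
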